## **4 Subject Selection and Withdrawal Criteria**

### **4.1 Selection of Study Population**

Approximately 156 subjects will be enrolled at 45 to 60 study centers in the United States and Canada. Subjects will be assigned to study treatment only if they meet all of the inclusion criteria and none of the exclusion criteria.

Deviations from the inclusion and exclusion criteria are not allowed because they can potentially jeopardize the scientific integrity of the study, regulatory acceptability, or subject safety. Therefore, adherence to the criteria as specified in the protocol is essential.

#### **4.1.1 Inclusion Criteria**

Each subject must meet all of the following criteria to be enrolled in this study:

1. Has a HVPG measurement  $\geq 6$  mm Hg.
2. Has a liver biopsy with advanced bridging fibrosis (Ishak stage 4) or cirrhosis (Ishak stage 5 or 6), presumably due to NASH. A liver biopsy diagnosis of advanced bridging fibrosis or cirrhosis, presumably due to NASH will include the following 2 categories:
  - a. Advanced bridging fibrosis or cirrhosis with a definitive pathological diagnosis of NASH (presence of fat, ballooning degeneration, and inflammation) or;
  - b. Advanced bridging fibrosis or cirrhosis wherein the subject has greater than 5 years of obesity (BMI  $>30$ ) and/or diabetes with negative viral hepatitis markers (hepatitis B and hepatitis C) and a biopsy showing any amount of fat.
3. Is  $\geq 18$  years of age and  $\leq 75$  years of age at the time of screening.
4. Is willing and able to provide written informed consent prior to the initiation of any study-specific procedures.
5. Is not pregnant and must have a negative serum pregnancy test result prior to randomization.

6. If a fertile man or woman participating in heterosexual relations, agrees to use effective means of contraception (ie, 2 effective methods of contraception, one of which must be a physical barrier method).
  - Effective forms of contraception include condom, hormonal methods (birth control pills, injections or implants), diaphragm, cervical cap, or intrauterine device throughout his/her participation in this study and for 90 days after discontinuation of study treatment. Surgically sterile males and females are not required to use contraception provided they have been considered surgically sterile for at least 6 months. Surgical sterility includes history of vasectomy, hysterectomy, bilateral salpingo-oophorectomy, or bilateral tubal ligation. Postmenopausal women who have been amenorrheic for at least 2 years at the time of screening will be considered sterile.
7. If a lactating woman, agrees to discontinue nursing before the start of study treatment and refrain from nursing until 90 days after the last dose of study treatment.
8. If a man, agrees to refrain from sperm donation throughout the study period and for a period of 90 days following the last dose of IMP. Female subjects may not begin a cycle of ova donation or harvest throughout the study period and for a period of 90 days following the last dose of IMP.
9. Prior to randomization, any subject on statins, angiotensin converting enzyme inhibitors, angiotensin II receptor blockers, or  $\beta$ -1 selective adrenergic receptor inhibitors should have been on a stable dose for at least 2 months and all attempts should be made to continue the subject on the same dose of the medication for the duration of study participation.

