### **6.1.2 Screening Visit (Week -8 to Day 0)**

The screening visit window is up to 8 weeks after the prescreening visit. Subjects who fail to meet eligibility criteria within this 8-week period due to an abnormal laboratory result may undergo retesting of the abnormal laboratory parameter during the screening window and at the discretion of the investigator and with prior approval of the medical monitor. During the screening visit, the following information will be collected ([Figure 3-2](#) and [Table 12-1](#)):

- Enter the IWRS and register subject visit data.
- Inclusion/exclusion criteria include AUDIT alcohol consumption questionnaire. The AUDIT is a screening tool to identify the early signs of hazardous and harmful drinking and identify mild dependence. This questionnaire (10 questions total) will be given to the subject at the beginning of the screening visit and will be considered source documentation. The subject will sign and date the questionnaire upon completion.
- Collect demographic information.
- Collect medical, surgical, and medication history (concomitant medications taken from 30 days prior to screening).
- Perform a 12-lead ECG assessment.
- Perform hematology testing.
- Perform blood chemistry testing.
- Perform coagulation profile.
- Obtain MELD score.
- Perform viral hepatitis B and C serology.
- Perform HIV serology.

- Perform urine drug screen for amphetamines, cocaine, and nonprescription opiates.
- Perform urinalysis testing.
- Perform serum pregnancy test (females of childbearing potential only).
- Perform chest radiograph (posterior-anterior and lateral views).
- Obtain Child-Turcotte-Pugh score and class (A, B, or C).
- Perform a complete physical examination (including height [in centimeters] and weight [in kilograms]) with particular attention to examination for stigmata of liver disease/cirrhosis.
- Collect vital sign measurements (including heart and respiratory rate, blood pressure, and body temperature).
- Perform MBT (if available) prior to EGD, HVPG, or liver biopsy (at the discretion of the investigator).
- EGD  
Subjects will have had an EGD within 2 months prior to randomization. Subjects with medium or large varices or varices with red signs (red wale marks or red spots), regardless of size, will be excluded from study participation. Subjects without varices or with small varices will continue to HVPG measurement and liver biopsy.
- Obtain demographic information.
- HVPG  

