### **6.1.3 Treatment Phase**

#### **6.1.3.1 Randomization**

Randomization must occur between 3 and 8 weeks after screening has begun. The IWRS will be used to administer the randomization schedule.

Prior to Infusion Visit 1, subjects with portal hypertension and the appropriate biopsy will be randomly assigned (1:1:1) to receive 1 of 3 treatment assignments: placebo, GR-MD-02 in dose of 2 mg/kg lean body mass, or GR-MD-02 in a dose of 8 mg/kg lean body mass. Subjects will be entered into the study and randomly assigned if they have both an HVPG screening measurement greater than or equal to 6 mm Hg and a liver biopsy with advanced bridging fibrosis (Ishak stage 4) or cirrhosis (Ishak stage 5 or 6), presumably due to NASH and meet all inclusion criteria and no exclusion criteria.

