#### **6.1.3.3 Infusion Visit 1 (Week 1)**

During the Infusion 1 Visit, the following procedures and assessments will be performed after randomization and prior to administration of IMP ([Table 12-2](#)):

- Enter the IWRS and register subject visit data.
- CLDQ (This questionnaire will be given to the subject at the beginning of the visit and will be considered source documentation.)
- Alcohol timeline followback (TLFB) (This will be given to the subject at the beginning of the visit and will be considered source documentation.)

- Perform a limited physical examination (including weight and examination of the heart, lung, and abdomen).
- Collect vital sign measurements (including heart and respiratory rate, blood pressure, and body temperature).
- Perform hematology testing.
- Perform blood chemistry testing.
- Collect biomarkers blood sample (will include the ELF test and FibroTest [FibroSure], and galectin-3).
- Collect plasma and serum sample for storage at  $-20^{\circ}\text{C}$ .

The following information will be collected after IMP administration:

- AE monitoring.
- Record concomitant medications.

The following will be performed 2 hours after the end of the IMP infusion:

- Collect PK sample.

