#### **6.1.3.4 Infusion Visits 2, 3, 4, 5, and 6 (Weeks 3, 5, 7, 9, and 11 $\pm$ 3 Days, respectively)**

The following procedures and assessments will be performed prior to administration of IMP:

- Enter the IWRS and register subject visit data.
- Alcohol TLFB (This will be given to the subject at the beginning of the visit and will be considered source documentation.) (Infusion Visit 5)
- Assessment of cirrhosis complications (Infusion Visits 3 and 5).
- Perform a limited physical examination (including weight and examination of the heart, lung, and abdomen).

- Collect vital sign measurements (including heart and respiratory rate, blood pressure, and body temperature).
- Perform urine pregnancy test (females of childbearing potential only) (Infusion Visits 3 and 5).

The following information will be collected after IMP administration:

- AE monitoring.
- Record concomitant medications.

The following will be performed 2 hours after the end of the IMP infusion

- Collect PK sample (Infusion Visits 2, 3, and 4)

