- e Urinalysis will include bacteria, bilirubin, blood, crystals, color, clarity, epithelial cells, glucose, hyaline and other casts, leukocyte esterase, nitrite, pH, specific gravity, ketones, protein, red blood cells, white blood cells, and yeast.
- f Serum pregnancy test for females of childbearing potential only. (A urine pregnancy test will be given every 4 weeks during the treatment phase.)
- g Including height (in cm) and weight (in kg) with particular attention to examination for stigmata of liver disease/cirrhosis).
- h Vital sign measurements include heart and respiratory rate, blood pressure, and body temperature. Blood pressure will be obtained with the subject in the supine position and measured twice consecutively with a 1-minute interval between measurements. The average of the 2 measurements will be recorded.
- i The MBT (if available) will be performed prior to EGD, HVPG, or liver biopsy (at the discretion of the investigator). The study center will make a follow-up telephone call to the subject to capture any AEs that may have occurred within 48 hours after the breath test.
- j Subjects will have had an EGD within 2 months prior to randomization. Subjects with medium or large varices or varices with red signs (red wale marks or red spots), regardless of size, will be excluded from study participation. Subjects without varices or with small varices will continue to HVPG measurement and liver biopsy.

Galectin Therapeutics Inc.

GR-MD-02 (galactoarabino-rhamnogalacturnate)

Protocol: GT-026 Original

20 February 2015

k Subjects must have both an HVPG measurement  $\geq 6$  mm Hg and a liver biopsy with advanced bridging fibrosis (Ishak stage 4) or cirrhosis (Ishak stage 5 or 6), presumably due to NASH. Subjects without varices or with small varices will have hepatic venous catheterization with measurement of both wedged and free hepatic venous pressures and standardized calculation of the HVPG prior to randomization and first IMP infusion.

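### No pregnancy test is scheduled between screening and Infusion Visit 3, so the first two infusions can rest on a serum result that is weeks old

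*Protocol*

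**What the plan says.** Protocol 4.1.1, inclusion 5, requires that a participant "Is not pregnant and must have a negative serum pregnancy test result prior to randomization". It ties the test to randomization, not to first dose, and gives no maximum age for the result.

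The serum test appears in the screening list (6.1.2): "Perform serum pregnancy test (females of childbearing potential only"). Table 12-1 places it in the same column, Week -8 to Day 0. Section 6.1.3.1 adds: "Randomization must occur between 3 and 8 weeks after screening has begun".

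At Infusion Visit 1 (6.1.3.3), "the following procedures and assessments will be performed after randomization and prior to administration of IMP". That list covers questionnaires, a limited examination, vital signs, hematology, chemistry, biomarkers and stored samples, but no pregnancy test. The urine pregnancy row of Table 12-2 is also empty at Visit 1.

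The first on-treatment entry is in 6.1.3.4: "Perform urine pregnancy test (females of childbearing potential only) (Infusion Visits 3 and 5"). It stands under the pre-dose heading "The following procedures and assessments will be performed prior to administration of IMP". Table 12-1 footnote f gives the frequency: "A urine pregnancy test will be given every 4 weeks during the treatment phase". Table 12-2 footnote d says the same. The SAP does not mention pregnancy testing.

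**The concern.** The protocol treats pregnancy as important. It bars entry, and under 6.4.6 a pregnancy during the study leads to discontinuation of study treatment (immediately, or as the sponsor directs) and a report within 24 hours. Yet no scheduled test confirms status at first exposure. Other information is refreshed at that point: weight, vital signs, hematology and chemistry at Visit 1, and FibroScan in the 2 weeks before it (6.1.3.2).

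What is at stake is participant and fetal safety. A pregnancy conceived after the serum test would go unnoticed by the schedule until Week 5, after two infusions.

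**Working it through.** Inputs, all from the Protocol:

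- Serum test at screening only (6.1.2, Table 12-1).
- Start of screening to randomization: 3 to 8 weeks, so L = 21 to 56 days (6.1.3.1).
- Infusions every 2 weeks (5.2). Visit v falls in Week 2v − 1, on Day 7(2v − 2) + 1.
- Urine tests at Visits 3, 5, 7, 9, 11, 13, 15, 17, 19, 21, 23 and 25 (6.1.3.4 to 6.1.3.11, Table 12-2).

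**1. The stated frequency.** The urine tests fall at Weeks 5, 9, 13, 17, 21, 25, 29, 33, 37, 41, 45 and 49. All 11 gaps are 4 weeks. From Visit 1 (Week 1) to the first test (Week 5) is also 4 weeks. The footnotes' frequency is reproduced.

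**2. Infusions before the first on-treatment test.** Visit 1 is Day 1, Visit 2 is Day 15 and Visit 3 is Day 29. The Visit 3 test precedes that day's dose, so two infusions (Weeks 1 and 3) come before it.

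**3. Gap between the serum test and the next test.** Assume the serum test is done on the first screening day and Infusion 1 follows randomization at once. The gap is L + (29 − 1) = L + 28 days:

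- Shortest lead: 21 + 28 = 49 days (7 weeks).
- Longest lead: 56 + 28 = 84 days (12 weeks).

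The Visit 3 window adds or removes up to 3 days.

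**4. Age of the latest result at each infusion, same assumptions.**

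| Infusion | Age of latest scheduled test |
|---|---|
| Visit 1 | L = 21 to 56 days |
| Visit 2 | L + 14 = 35 to 70 days |
| Visit 3 | 0 days |
| Visit 4 | 14 days |
| Visits 5 to 26 | alternates 0 and 14 days |

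Every later 4-week interval also holds two infusions. What sets the first two apart is the age of the result they rest on.

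**5. Sensitivity.** A serum test done t days into screening shortens the gap, and the ages at Visits 1 and 2, by t days. At the extreme, a serum test on the day of first dosing leaves 28 days to the next test. A delay between randomization and Infusion 1 lengthens them. No explicit limit on that delay is stated, although the synopsis total of 1 + 8 + 52 + 6 = 67 weeks leaves no room for one.

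The prose and the tables agree, so the empty Visit 1 cell is not a fault of text extraction. No expected number of affected women can be given: the documents state neither how many are of childbearing potential nor a conception rate.

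**The case against.** The strongest reply is that the documents are consistent and already contain safeguards. Much of this stands.

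- A reader might infer that the every-4-weeks footnote is breached, because 84 days is three times 28. It is not. The footnote covers the treatment phase only, and the schedule meets it from Week 1 onward. The long gap arises by adding screening time.
- A reader might infer that any woman who conceives during screening will be dosed. The serum test may be done at any time in screening, so a conception before a late test may be detected. The exposure needs conception after the serum test.
- Inclusion 6 requires two contraceptive methods, one a physical barrier, throughout participation, and Protocol 4.2 counts the study from consent. The synopsis instead ties contraception to the treatment period plus 90 days, so the two places need reconciling. Either way, contraception lowers the probability of pregnancy and does not reveal one.
- Inclusion 5 separately requires that the participant not be pregnant, and 4.1 allows no deviations. No scheduled test verifies this at randomization or first dose unless the serum test happens to fall late. Unscheduled testing is permitted but not required.
- The Protocol in hand is the original of February 2015, while the SAP describes some later features, such as nondosing PK visits. The schedule finally used may differ, so the point is limited to the text available.

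**Conclusion.** The point holds as a gap in the safety schedule, not as a contradiction between passages. Two infusions can be given before any scheduled repeat test. On the assumptions in the working, the serum result is 21 to 56 days old at the first infusion and the gap between tests is 49 to 84 days, plus or minus 3. These are the values for a test on the first screening day; later testing reduces them. The change is worth making because it is cheap and closes the gap at first exposure.

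A reader might go further and infer that the primary HVPG analysis is compromised. The documents do not support that. The sample size and type I error rate are untouched, and the number of women concerned is unknown. Protocol 4.2.2 asks for end-of-study assessments whenever possible after discontinuation, although SAP 3.1 asks for HVPG in early terminators only after at least 13 infusions. SAP 8.1.1 includes an analysis with the last observation carried forward. A test at Visit 1 after randomization would not in any case prevent such a loss, since the woman would already be randomized.

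**What to change.** Add the urine pregnancy test already used from Visit 3 (females of childbearing potential) to the pre-dose procedures in Protocol 6.1.3.3 and to the Visit 1 cell of the urine test row in Table 12-2. Where randomization and Infusion Visit 1 fall on the same day, have the result known before randomization.

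Leave inclusion 5 assessable before randomization. Rewriting it to depend on a test before the first infusion would create an entry criterion that can be judged after randomization, in conflict with 4.1 and 6.1.3.1.

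The sponsor should reconcile 4.1.1, 6.1.3.1, 6.1.3.3, 6.4.6 and Table 12-2 on how a positive result is handled; no handling rule is proposed here. If Visit 1 falls on a later day than randomization, a positive result would concern a participant who is already in the full-analysis set and, if discontinued, is not replaced (4.2.3). The reconciled text should cover that case.

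The cost is one urine kit per woman of childbearing potential and one schedule entry. No new visit or type of procedure is needed.

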#### **4.1.2 Exclusion Criteria**

Subjects meeting any of the following criteria will be excluded from the study:

1. Has a history of hepatic decompensation including any episode of variceal bleeding, clinically detectable ascites, or overt hepatic encephalopathy (defined by the clinical judgment of the principal investigator but should include the presence of lethargy, disorientation, inappropriate behavior, and the presence of asterixis).

2. Has a presence of medium or large varices or varices with red signs regardless of size based on endoscopy.
  - Small varices are defined by veins that occupy >25% of the distal one third of the esophageal lumen when insufflated. Veins that completely flatten upon insufflation of the esophagus are not considered varices. Any varices larger than that are medium (up to 50%) or large (>50%).
  - Red signs include red wale markings (dilated venules oriented longitudinally on the variceal surface), cherry red spots (small, red, spotty dilated venules usually approximately 2 mm in diameter on the variceal surface) or hematocystic spots (large, round, crimson red projection >3 mm that look like a blood blister on the variceal surface).
3. Has had a prior transjugular porto-systemic shunt procedure.
4. Has evidence of other forms of chronic liver disease including viral hepatitis B or C, primary biliary cirrhosis, primary sclerosing cholangitis, Wilson's disease, alpha-1 antitrypsin deficiency, alcoholic hepatitis, hemochromatosis, liver cancer, history of biliary diversion, or autoimmune hepatitis.
5. Has any of the following laboratory values:
  - a. Serum alanine aminotransferase levels  $>10 \times$  the upper limits of normal
  - b. Serum aspartate aminotransferase levels  $>10 \times$  the upper limits of normal
  - c. Serum creatinine  $\geq 2.0$  mg/dL
  - d. Platelet count  $<60\,000/\text{mm}^3$
  - e. Serum albumin  $\leq 2.8$  g/dL
  - f. International normalized ratio (INR)  $\geq 1.7$
  - g. Direct bilirubin  $\geq 2.0$  mg/dL
6. A MELD score  $\geq 15$  or Child-Turcotte-Pugh Class B or C.

7. Is unwilling or unable to safely undergo HVPG or liver biopsy.
8. Has known positivity for human immunodeficiency virus (HIV) infection or a positive HIV test result at screening.
9. Has had major surgery within 8 weeks of randomization, significant traumatic injury within 6 months, or anticipation of need for major surgical procedure during the course of the study.
10. Has a history of a solid organ transplant requiring current immunosuppression therapy.
11. Has used nonselective  $\beta$ -adrenergic inhibitors within 6 weeks prior to randomization or at any time during the study.
12. Has planned or anticipated variceal ligation therapy during the study.
13. Has had weight reduction surgery within the past 3 years or plans to undergo weight reduction surgery during the study.
14. Has current, significant alcohol consumption or a history of significant alcohol consumption for a period of more than 3 consecutive months any time within 1 year prior to screening.
  - Significant alcohol consumption is defined as more than 20 grams per day in females and more than 30 grams per day in males. On average, a standard drink in the United States is considered to be 14 g of alcohol equivalent to 12 fluid oz of regular beer (5% alcohol), 5 fluid oz of table wine (12% alcohol), or 1.5 fluid oz of 80 proof spirits (40% alcohol). A score of  $\geq 8$  on the Alcohol Use Disorders Identification Test (AUDIT) (Babor 2000) will result in exclusion. (The AUDIT is provided in [Section 12.2.](#))
15. Has a positive urine screen result for amphetamines, cocaine, or nonprescription opiates (heroin, morphine) at screening.

16. Has clinically significant and uncontrolled cardiovascular disease (eg, uncontrolled hypertension, myocardial infarction within 6 months prior to randomization, unstable angina), New York Heart Association Grade II or greater congestive heart failure, serious cardiac arrhythmia requiring device/ablation or Grade II or greater peripheral vascular disease within 12 months prior to randomization.
17. Has a history of clinically significant hematologic, renal, hepatic, pulmonary, neurological, psychiatric, gastrointestinal, systemic inflammatory, metabolic or endocrine disorder or any other condition that, in the opinion of the investigator, renders the subject a poor candidate for inclusion into the study.
18. Has concurrent infection including diagnoses of fever of unknown origin at the time of randomization (subjects must be afebrile at the start of therapy).
19. Has a history of malignancy, except for the following adequately treated nonmetastatic basal cell skin cancer; any other type of skin cancer, except melanoma, that has been adequately treated and has not recurred for at least 1 year prior to enrollment; and adequately treated in situ cervical cancer that has not recurred for at least 1 year prior to screening.
20. Participates in an investigational new drug study within 30 days prior to randomization (including follow-up visits) or at any time during the current study.
21. Has a clinically significant medical or psychiatric condition considered high risk for participation in an investigational study.
22. Fails to give informed consent.
23. Has known allergies to the IMP or any of its excipients.
24. Is an employee or family member of the investigator or study center personnel.
25. Needs concomitant use of drugs with a narrow therapeutic window metabolized by cytochrome P450 3A4 (CYP3A4) isozyme including specifically the fast-acting opioids alfentanil and fentanyl; the immunosuppressive drugs cyclosporine, sirolimus, and tacrolimus; the cardiovascular agents ergotamine, quinidine, and dihydroergotamine; and the psychotropic agent pimozone.

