## **4.2 Withdrawal of Subjects from the Study**

The duration of the study is defined for each subject as the date a signed written informed consent is provided through the last follow-up visit, up to 42 days following the last IMP infusion.

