Subjects must have both an HVPG measurement  $\geq 6$  mm Hg and a liver biopsy with advanced bridging fibrosis (Ishak stage 4) or cirrhosis (Ishak stage 5 or 6), presumably due to NASH. Subjects without varices or with small varices will have hepatic venous catheterization with measurement of both wedged and free hepatic venous pressures and standardized calculation of the HVPG prior to randomization and first IMP infusion.

- Obtain liver biopsy  
Liver biopsy may be obtained via a percutaneous approach or a transjugular approach during the HVPG procedure, at the preference of the investigator.
- AE monitoring.

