### **6.2.7 EGD Evaluation**

Subjects will undergo an EGD within 2 months prior to randomization and within 14 to 28 days after the final 26th dose of IMP or where feasible following study termination and the following information will be collected.

Esophageal varices, if present, will be classified as follows:

1. Large varices >50% impingement on the lumen;
2. Small varices <25% impingement on lumen;
3. Medium varices are intermediate between small and large varices.

Subjects with medium or large varices or varices with red signs, regardless of size, will be excluded from study participation. Red signs include red wale markings (dilated venules oriented longitudinally on the variceal surface), cherry red spots (small, red, spotty dilated venules usually about 2 mm in diameter on the variceal surface) or hematocystic spots (large, round, crimson red projection greater than 3 mm that looks like a blood blister on the variceal surface). Subjects without varices or with small varices will advance to HVPG measurement and liver biopsy. Consistent with the American Association for the Study of Liver Disease practice guidelines ([Garcia-Tsao 2007](#)), subjects with small varices will not receive treatment

with nonselective  $\beta$ -adrenergic inhibitors or variceal ligation therapy during the clinical study since long-term benefit has not been established for small varices. At the discretion of the principal investigator, subjects who have no varices or small varices and are currently on  $\beta$ -adrenergic inhibitors may be withdrawn from therapy at least 4 weeks prior to randomization.

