### **10.2.2 Protocol Deviations**

The investigator or designee must document and explain in the subject's source documentation any deviation from the approved protocol. The investigator may implement a deviation from, or a change of, the protocol to eliminate an immediate hazard to study subjects without prior IRB/IEC approval. As soon as possible after such an occurrence, the implemented deviation or change, the reasons for it, and any proposed protocol amendments should be submitted to the IRB/IEC for review and approval, to the sponsor for agreement, and to the regulatory authorities, if required.

A deviation from the protocol is an unintended or unanticipated departure from the procedures or processes approved by the sponsor and the IRB/IEC and agreed to by the investigator. A significant deviation occurs when there is nonadherence to the protocol by the subject or investigator that results in a significant, additional risk to the subject. Significant deviations can include nonadherence to inclusion or exclusion criteria, enrollment of the subject without prior sponsor approval, or nonadherence to FDA regulations or ICH E6(R1) GCP guidelines, and will lead to the subject being withdrawn from the study ([Section 4.2](#)).

Protocol deviations will be documented by the clinical monitor throughout the course of monitoring visits. Principal investigators will be notified in writing by the monitor of deviations. The IRB/IEC should be notified of all protocol deviations in a timely manner.

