8.1. Primary Efficacy Endpoint

HVPG will be collected at screening and 14 to 28 days after final dose (53-55 weeks), and used as a measure of portal hypertension. Both wedged hepatic venous pressure (WHVP) and free hepatic venous pressure (FHVP) will be measured for subjects without varices or with small varices. HVPG is defined as the difference between the WHVP and the FHVP. A single experienced investigator, [name] (Yale University), will evaluate all HVPG tracings at a central reading facility.

The HVPG will be summarized for the FAS population by visit and treatment group, for all scheduled visits, along with the change from baseline descriptively in a summary table and graphically. In addition, the number and percentage of subjects will be summarized by the following HVPG categories (mild portal hypertension (MPH) ie ≥ 6 mmHg to < 10 mmHg and clinically significant portal hypertension (CSPH) ie ≥ 10 mmHg).

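### Section 6.2.7 lets beta-blockers be stopped 4 weeks before randomization where exclusion 11 requires 6, and neither protocol nor SAP sets a drug-free time before the baseline HVPG

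*Protocol*

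**What the plan says.** Four sets of provisions bear on this.

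- **Eligibility.** Protocol 4.1.2, exclusion 11, bars nonselective beta-adrenergic inhibitors "within 6 weeks prior to randomization or at any time during the study". Protocol 4.1 adds: "Deviations from the inclusion and exclusion criteria are not allowed". Section 6.1.3.1 likewise limits randomization to subjects who meet every inclusion criterion and no exclusion criterion. Inclusion 9 (4.1.1) treats beta-1 selective agents differently: the dose should have been stable for at least 2 months and should be kept if possible.
- **Withdrawal.** Protocol 6.2.7 says that, at the principal investigator's discretion, subjects with no varices or small varices who are taking beta-adrenergic inhibitors "may be withdrawn from therapy at least 4 weeks prior to randomization". This sentence does not say nonselective.
- **Timing.** Section 6.1.3.1: "Randomization must occur between 3 and 8 weeks after screening has begun". Section 6.1.2 requires, after the EGD has shown no or only small varices, hepatic vein catheterization and "standardized calculation of the HVPG prior to randomization and first IMP infusion". SAP 8.1 takes the HVPG at screening and again 14 to 28 days after the last dose. SAP section 4 defines baseline as the last value before the first infusion, so the screening HVPG is the primary-endpoint baseline.
- **Start of the study.** Protocol 4.2: "The duration of the study is defined for each subject as the date a signed written informed consent is provided". Section 5.10 prohibits nonselective agents for portal hypertension during the study and gives no washout length.

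**The concern.** The two sections give sites different minimum intervals for the same action. A coordinator who works from 6.2.7 may stop the drug, arrange EGD, catheterization and biopsy, and then find that exclusion 11 fails. Because 6.2.7 omits the word nonselective, it could also be read as inviting withdrawal of the beta-1 selective agents that inclusion 9 wants kept stable.

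The second part concerns the measurement. Protocol 7.6 treats nonselective beta-blockers as HVPG-lowering therapy, so residual drug effect at baseline matters. The washout is tied to randomization, yet the value to be protected is the HVPG taken earlier in screening. That value decides entry at 6 mm Hg, defines change from baseline, is the ANCOVA covariate, and sets the 10 mm Hg split between mild and clinically significant portal hypertension used in SAP 8.1 and 8.1.1. A reading on drug, or soon after stopping, may not represent the untreated pressure that the trial sets out to follow.

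**Working it through.** The plan gives no figure to reproduce here. The check is timeline arithmetic on its stated windows.

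**Inputs.** Randomization at week R of screening, R from 3 to 8 (6.1.3.1). Required time off drug before randomization, w: 6 weeks (exclusion 11) or 4 weeks (6.2.7).

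**Step 1: where the rules conflict.** For a drug stopped s weeks into screening, the rule is R − s ≥ w, so s ≤ R − w. At the latest permitted R of 8:

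- exclusion 11: s ≤ 8 − 6 = 2
- section 6.2.7: s ≤ 8 − 4 = 4

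A stop after week 2 and up to week 4 can satisfy 6.2.7 but can never satisfy exclusion 11. A stop on the first day of screening (s = 0) satisfies 6.2.7 for R from 4 to 8 and exclusion 11 only for R from 6 to 8, so the rules disagree for R from 4 to under 6. In general they disagree for anyone stopped 4 to under 6 weeks before randomization.

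**Step 2: drug-free time at the baseline HVPG.** If the HVPG is taken h weeks before randomization and the drug is stopped exactly w weeks before, drug-free time at HVPG is w − h. A negative value means that the drug is still being taken.

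| HVPG, weeks before randomization (h) | w = 6 | w = 4 |
|---|---|---|
| 8 | −2 | −4 |
| 6 | 0 | −2 |
| 5 | 1 | −1 |
| 4 | 2 | 0 |
| 3 | 3 | 1 |

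Example: HVPG at week 0, drug stopped at week 2, randomization at week 8. The 6-week count is met (8 − 2 = 6), although the HVPG was taken on drug.

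**Step 3: the meaning of the on-study ban in exclusion 11.** Step 2 applies if the study is taken to start at randomization. If it starts at consent, as 4.2 suggests, any use at the screening HVPG is barred. Two gaps remain. The drug-free time can then be as short as the interval from consent to HVPG, for which no minimum is set. And a subject still on drug at consent is already excluded, so the withdrawal described in 6.2.7 has no consented subject to apply to.

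**Step 4: search for a separate rule.** Protocol 6.1.2, 6.2.1, 5.10 and the footnotes to Table 12-1, and SAP 8.1, give no beta-blocker-free interval before HVPG. Section 6.2.1 refers HVPG procedure to the Study Manual.

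**The case against.** The strongest reply is that exclusion 11 settles the matter. Section 6.2.7 is discretionary and sets a floor, so stopping 6 weeks or more beforehand satisfies both. Sections 4.1 and 6.1.3.1 leave no doubt that eligibility criteria take precedence. That stands, and it limits the consequence: 6.2.7 does not authorize enrolling an ineligible subject. What remains is that a site is told 4 weeks is enough and finds out otherwise after acting on it.

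A reader might go further and infer that such subjects would become significant deviations and drop out of the per-protocol set. Section 10.2.2 does say "Significant deviations can include nonadherence to inclusion or exclusion criteria", but it defines a significant deviation by significant added risk to the subject. Nothing in the documents shows that 4 or 5 weeks off drug rather than 6 carries such risk, so that chain is not supported.

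On the HVPG part, the reply is that the consent-based definition in 4.2 already prevents an on-drug baseline and that the Study Manual may contain a washout rule. Both are fair. The first does not prevent a short washout and makes 6.2.7 unusable. The second cannot be checked, so this part is limited to what the protocol and SAP state. A manual rule would in any case not reconcile 6.2.7 with exclusion 11.

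A reader might also infer a biased treatment effect or a material loss of power. Randomization makes any on-drug or short-washout baselines similar across arms in expectation. The documents give neither the share of subjects affected nor the shift in HVPG, so no loss of power can be calculated.

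**Conclusion.** The mismatch between 4 and 6 weeks is certain on the text, as are the missing word in 6.2.7 and the absence from protocol and SAP of a drug-free interval tied to the baseline HVPG. The practical results are avoidable screen failures or eligibility deviations, some added noise in the primary baseline, and possible misclassification at the 6 and 10 mm Hg cuts. No systematic bias between arms is expected, and the size cannot be derived from the documents. Severity is minor.

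Two limits apply. The Study Manual was not available. The protocol reviewed is the original of 20 February 2015, while the SAP already reflects later changes, such as enrolling only Ishak stage 5 or 6, so a later protocol version may have corrected this. The sponsor should confirm which interval was applied.

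**What to change.** - In 6.2.7, write nonselective beta-adrenergic inhibitors, and replace 4 weeks with at least 6 weeks.
- In 6.1.2 and 6.2.1, require the baseline HVPG to be taken after that same 6-week washout. Because HVPG precedes randomization, this also satisfies the 6-week interval in exclusion 11.
- In exclusion 11, state that withdrawal under 6.2.7 is allowed if this washout is met.

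This is a clarifying amendment of a few sentences. Protocol 5.9 already records all prior treatments for cirrhosis without the 30-day limit that applies to other drugs, so use for portal hypertension should be captured without a new data item.

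The cost falls on the few affected subjects. Withdrawal follows the EGD, since 6.2.7 restricts it to those with no or small varices. With EGD and withdrawal both on the first screening day, 56 − 42 = 14 days remain for HVPG, central reading, biopsy and randomization. Some subjects may not fit the window.
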